7.4.3.2.2 Sponsor's responsibilities

The Sponsor will ensure the reporting of SUSARs and any expeditable SAEs to regulatory Authorities, ECs/IRB in accordance with applicable laws.

In the event of a SUSAR, the Sponsor will ensure that Investigators active in Basilea-sponsored interventional studies with derazantinib are informed.

Expectedness of SAEs for regulatory expedited reporting will be assessed by the Sponsor against the applicable study drug Reference Safety Information (RSI).

For both derazantinib and atezolizumab the 'Reference Safety Information' Section in the relevant Investigator's Brochures (valid at the time of onset of the event) will serve as the RSI.

7.4.4 Handling of post-study safety data

After the Safety Follow-up visit(s), only study drug related SAEs and AESIs (see Section 7.2.6) should be collected and reported; however, these events should not be captured in the eCRF system.

New study drug related SAEs and AESIs that occur after the 28-day Safety Follow-up visit (or 90-day Safety Follow-up visit for atezolizumab-treated patients) will be followed until they have, in opinion of the Investigator, resolved to baseline, CTCAE grade 1, stabilized, or are deemed to be irreversible (including death).and if the patient withdraws their consent.

7.4.5 Reporting and handling of pregnancies

Female patients must inform the Investigator within 24 hours if they have experienced a ruptured condom, or any other concerns about possible reduction of contraceptive effectivity (i.e., forgotten pill or vomiting) during the study. In these cases, the patients must return to the study site as soon as possible, but not later than 24 hours after the Investigator is informed, for adequate medical measures and follow-up visits.

Female patients must inform the Investigator if they become pregnant during the study, or within 150 days after the last dose of study drug.

Study drug(s) must be discontinued immediately if a female patient becomes pregnant.

The Investigator should counsel the patient, discussing the risks of the pregnancy and the possible effects on the fetus. The patient must be monitored until conclusion of the pregnancy and infants must be followed-up for at least 8 weeks after delivery. Any SAEs associated with the pregnancy (e.g., an event in the fetus, an event in the mother during or after the pregnancy, or a congenital anomaly/birth defect in the child) should be reported on the AE eCRF and in pregnancy and SAE form.

The Investigator must immediately notify the Sponsor's safety representative about any pregnancy by submitting a Pregnancy Report Form, in accordance with the requirements (timelines and contact details) of an SAE (see Section 7.4.3.2). In addition, pregnancy-related adverse outcomes must also be reported as AEs or SAEs (see Section 7.4.3.1). Note that an induced abortion which is not due to an AE does not constitute an SAE.

Male patients will be instructed through the information provided in the ICF to immediately inform the Investigator if their partner becomes pregnant during the study. A Pregnancy Report Form should be completed by the Investigator immediately (i.e., no more than 24 hours after learning of the pregnancy). Attempts should be made to collect and report details of the course and outcome of any pregnancy in the partner of a male patient exposed to study drug. The pregnant partner will need to sign the appropriate authorization to allow for follow-up on her pregnancy. Once the authorization has been signed, the Investigator will update the Pregnancy Report Form with additional information on the course and outcome of the pregnancy.

An Investigator who is contacted by the male patient or his pregnant partner may provide information on the risks of the pregnancy and the possible effects on the fetus to support an informed decision in cooperation with the treating physician and/or obstetrician.

The Investigator must notify the local IEC/IRB about any pregnancies resulting in an adverse outcome, in accordance with applicable laws and regulations.

7.5 Adverse events associated with an overdose or error in drug administration

An overdose is the accidental or intentional use of a drug in an amount higher than the dose being studied.

A medication error is an unintended failure in the drug treatment process that leads to, or has the potential to lead to, harm of the patient.

Any overdose or medication error (with or without AE) should be recorded in the eCRF.

All AEs associated with an overdose or medication error should be recorded on the eCRF (see Section 7.4.3.1). If the associated AE fulfils seriousness criteria, the event should be reported to the Sponsor immediately (see Section 7.4.3.2).

8 STATISTICAL CONSIDERATIONS AND ANALYTICAL PLAN

Effective Protocol Version 5.0, only statistical considerations applicable to active substudies are provided in this section.

Details of the statistical analyses presented below will be provided in the study's statistical analysis plan (SAP). A change to the data analysis methods described in the protocol will require a protocol amendment only if it alters a principal feature of the protocol. The SAP will be finalized prior to database lock. Any changes to the methods described in the plan will be described and justified in the final clinical study report.

8.1 Sample size considerations by substudy

Simon's two-stage designs ([Simon 1989](#)) will be used for **Substudies 1 and 4**, and Fleming's two-stage designs ([Fleming 1982](#)) will be used for **Substudies 3 and 5**. At the time point of interim analysis and decision to transition from Stage 1 to 2, all data collected in Stage 1 patients will be used to inform the decision. Should the required number of events (i.e., responses) be reached prior to full enrollment to Stage 1, the time point for decision to transition from Stage 1 to Stage 2 may be taken before the stage is fully enrolled. If the required number of events (i.e., responses) is not reached at the time of full enrollment to Stage 1, further enrollment may be suspended to allow for all patients to be exposed to derazantinib or derazantinib-atezolizumab in combination for at least 3 months or until disease progression.

The use of such designs will limit the number of overall exposed patients to a maximum of approximately 98, should either derazantinib or derazantinib-atezolizumab in combination be ineffective in Stage 1 of all efficacy-estimating substudies, as compared to a maximum of 246 patients if derazantinib or derazantinib-atezolizumab are considered to be effective in all cohorts.

Assuming an overall incidence of approximately 20% qualifying *FGFR1-3* GAs ([Helsten 2016](#)), up to approximately 680 patients will be screened for *FGFR1-3* GAs, depending on the extent of preexisting molecular testing. Assuming that pre-treatment with an FGFR inhibitor was based on a known *FGFR* GA status, no repeated testing is anticipated for the approximately 100 patients enrolled in Substudy 4.

8.1.1 Substudy 1

The null hypothesis that the true ORR is $p_0 \leq 0.21$ will be tested against a one-sided alternative. In Stage 1, 35 evaluable patients will be enrolled. If 7 or fewer patients with an objective response are observed in Stage 1, the cohort will be stopped. If 8 or more patients with an objective response (defined as a CR or PR) are observed in these 35 patients, an additional 39 patients will be enrolled, for a total of 74 patients. The null hypothesis will be rejected if 22 or more responses are observed in these 74 patients. The one-sided Type I error rate is 0.0463, and the power is 0.8001 when the true ORR is $p_1 = 0.34$ and higher than the ORR of 32.2%, the highest reported value for an FGFR inhibiting treatment in mUC patients ([Balversa USPI](#)).

The ORR of 21% for the null hypothesis reflects the lower range of ORR seen in recent clinical studies of UC patients with FGFR GAs (Loriot 2019, Necchi 2018, Pal 2018).

8.1.2 Substudy 3

The Fleming’s two-stage design sample size calculation is based on the assumption that first-line cisplatin-ineligible patients with advanced or metastatic mUC expressing *FGFR1–3* GAs treated with 200 mg BID derazantinib in combination with 1200 mg atezolizumab Q3W will attain a clinically meaningful ORR of approximately 45%, which is similar to that obtained with erdafitinib and cetrelimab (Moreno 2020), or rogaratinib and atezolizumab (Rosenberg 2020), in combination for this patient population, and is considered the benchmark by oncology experts. An ORR of 25% (estimated mean ORR with immune checkpoint-inhibiting monotherapy available for cisplatin-ineligible patients) is not considered sufficiently effective to warrant further clinical investigation.

Using a Fleming’s two-stage design, a total sample size of 36 is required to test a null hypothesis of $H_0: \pi \leq 0.25$ versus an alternative hypothesis of $H_a: \pi \geq 0.45$ with a one-sided target significance level of 0.05 and target power of 80%, where π is the true proportion of successes. This design results in an exact type 1 error rate of 0.046, an exact level of power of 81%, and an average sample size of 27 patients under H_0 and 31 under H_a . Table 7 summarizes the required samples sizes and required responses to either accept or reject H_0 .

Table 7 Summary of sample size and required responses of proposed two-stage Fleming design

	Sample size		Responders to accept H_0		Responders to reject H_0	
	N	n	%	n	%	
Stage 1	18	4	22.2	10	55.6	
Stage 2	36	13	36.1	14	38.9	

8.1.3 Substudy 4, Cohorts 4a and 4b

For both cohorts within Substudy 4, the null hypothesis that the true ORR is $p_0 \leq 0.07$ will be tested against a one-sided alternative. In Stage 1 of each cohort, 16 evaluable patients will be enrolled. If 1 or fewer patients with an objective response are observed in these 16 patients, the cohort will be stopped. If 2 or more patients with an objective response are observed, an additional 34 patients will be enrolled for a total of 50. The null hypothesis will be rejected if seven or more responses are seen in these 50 patients. Type I error rate is 0.0448 and power is 0.8027 when true ORR is $p_1 = 0.20$.

The ORR of 7% for the null hypothesis reflects the ORR reported based on literature of retrospective data and/or small cohorts of uncontrolled studies (Di Lorenzo 2015, Soga 2010) for *FGFR1–3* GA expressing UC patients treated with third or fourth-line single-agent chemotherapy with prior progression following platinum-containing chemotherapy, immune-checkpoint blockade and/or FGFR inhibitor treatment.

8.1.4 Substudy 5

The Fleming's two-stage design sample size calculation is based on the assumption that patients with mUC expressing *FGFR1-3* GAs, after failure of prior platinum- or immune-checkpoint-inhibitor-containing treatment, treated with 200 mg BID derazantinib will attain a clinically meaningful ORR of approximately 30%. This is similar to that obtained with erdafitinib for this patient population, and considered the benchmark by oncology experts. An ORR of 10% is not considered sufficiently effective to warrant further clinical investigation.

Using a two-stage Fleming design, a total sample size of 26 is required to test a null hypothesis of $H_0: \pi \leq 0.1$ versus an alternative hypothesis of $H_a: \pi \geq 0.3$ with a one-sided target significance level of 0.05 and target power of 80%, where π is the true proportion of successes. This design results in an exact type 1 error rate of 0.039, an exact level of power of 81.9%, an average sample number of 18 patients under H_0 and of 21 under H_a . [Table 8](#) summarizes the required samples sizes and required responses to either accept or reject H_0 .

Table 8 Summary of sample size and required responses of proposed two-stage Fleming design

	Sample size	Responders to accept H_0		Responders to reject H_0	
	N	N	%	n	%
Stage 1	13	1	7.7	5	38.5
Stage 2	26	5	19.2	6	23.1

8.2 Analysis populations

The following analysis populations are defined for this study:

8.2.1 Safety analysis population / Intent-to-treat population

The Safety / Intent-to-treat population consists of all patients with an eligible *FGFR1-3* GA who received at least one dose of derazantinib or atezolizumab. Safety data will be summarized according to the treatment actually received.

In the primary safety comparison, patients who crossover to derazantinib-atezolizumab combination are censored at time of crossover (i.e., AEs occurring during treatment with derazantinib-atezolizumab combination are excluded for Cohort 4a patients). An exploratory safety analysis will be conducted for the crossover population including all safety events starting from the date of the first dose of derazantinib-atezolizumab combination.

8.2.2 Modified intent-to-treat population

For all efficacy endpoint analyses, a mITT population will be used, comprising all patients who received at least one dose of derazantinib or atezolizumab, and have at least one post-baseline imaging assessment in accordance with RECIST 1.1, or documented clinical

progression (every effort should be made to objectively assess radiographic progression). Non-evaluable patients will be replaced.

8.2.3 Per-protocol population

The Per-protocol population will include all patients in the mITT population who have no major protocol deviations during the study. Protocol deviations will be identified prior to final analysis.

This analysis population will be used for secondary analysis of primary and secondary endpoints.

8.2.4 Pharmacokinetic analysis population

The PK analysis population consists of all patients who receive at least one dose of derazantinib and have at least one PK sample. Three sub-populations are defined, according to the analytes and sampling schedule:

- The Rich derazantinib PK profiling population (with PK parameter determination) consists of the patients enrolled in the rich sampling schedule (see Section 5.3.4.1.2) who receive at least 1 dose of study drug and have at least one PK sample.
- The Sparse derazantinib PK sampling population consists of the patients enrolled in the sparse sampling schedule (see Section 5.3.4.1) who receive at least 1 dose of study drug and have at least one PK sample.
- The atezolizumab PK population (see Section 5.3.4.2) consists of all patients who receive at least 1 dose of atezolizumab and have at least one PK sample.

8.3 Statistical and analytical methods

All endpoints will be summarized by substudy and cohort. All analyses will include summary statistics, including number and percentage for categorical variables, and number of patients, mean, standard deviation, median, minimum, and maximum for continuous variables. Two-sided 95% confidence intervals (CIs) will be provided where appropriate, except otherwise specified. Time-to-event analysis will be performed using Kaplan-Meier (KM) methods. Further detail will be provided in the study SAP.

All analyses will be carried out using SAS[®] version 9.3 or above (SAS Institute, Cary, North Carolina, USA).

8.3.1 Patient demographics, medical history, and other baseline characteristics

Demographics, medical history, and other baseline characteristics will be summarized for the safety/ITT, mITT and Per-protocol (PP) populations using descriptive statistics. No formal statistical comparisons will be performed.

Demographic, baseline characteristics, and medical history data for each patient will be provided in data listings.

8.3.2 Study treatment exposure and compliance

The dose, duration in days and compliance of study treatment(s) will be listed by patient and summarized through descriptive statistics by cohort in the Safety population.

8.3.3 Prior and concomitant treatments

Medications and significant non-drug therapies used prior to and after the start of the study drug will be listed by patient and summarized by Anatomical Therapeutic Chemical term and by cohort.

8.3.4 Efficacy analysis

All efficacy endpoints will be summarized by substudy and cohort.

All analyses will include summary statistics, including number of patients and percentage for categorical variables and number of patients, mean, standard deviation, median, minimum, and maximum for continuous variables. Two-sided exact 95% CIs based on the large sample assumption will be provided where appropriate.

Comparisons between cohorts of **Substudy 4** will be performed using descriptive statistics and for the purpose of hypothesis generation.

8.3.4.1 Primary endpoint

The primary endpoint in all substudies will be ORR, defined as the achievement of confirmed CR or PR using RECIST 1.1, as assessed by BICR. Point estimates and 2-sided 95% CIs will be provided. The primary analysis will be performed on the mITT population and repeated on the PP population.

Interim analyses for stage transition in the efficacy-estimating substudies will be performed when the number of patients specified below have been enrolled, have received at least one dose of study drug, and have at least had one post-baseline tumor imaging assessment, but no later than after the completion of Cycle 9 (i.e., have received approximately 27 weeks of treatment and had up to four post-baseline study imaging assessments). If the required number of responses per BICR specified for each cohort has not been observed at the time of enrollment of the last patient to Stage 1, enrollment may be suspended, or the cohort may be terminated due to apparent futility.

If the required number of responses per BICR specified for each cohort is reached earlier, interim analyses may be performed earlier.

The final analysis for ORR will be performed once all patients have been enrolled per cohort/substudy and have been followed for approximately up to 27 weeks of treatment (i.e., each patient had up to four post-baseline study imaging assessments). Patients without efficacy assessments are considered non-responders, and included in the analysis. Hypothesis testing (null hypothesis [H_0] versus alternative hypothesis [H_A]) will be performed at the interim and final analyses as per the below specified decision rules:

- **Substudy 1**

H_0 : $p \leq 0.21$ versus H_A : $p > 0.21$.

If there are five or fewer patients with a response (defined as a CR or PR) in the first 35 evaluable patients included in the interim analysis, the substudy will be stopped. If not, an additional 39 patients will be enrolled, for a total of 74 evaluable patients. The null hypothesis will be rejected if 22 or more responses are observed in these 74 patients.

- **Substudy 3**

$H_0: p \leq 0.25$ versus $H_A: p > 0.45$.

If there are four or fewer patients with a response (defined as a CR or PR) in the first 18 evaluable patients included in the interim analysis, the cohort will be stopped. If not, an additional 18 patients will be enrolled, for a total of 36 evaluable patients. The null hypothesis will be rejected if 14 or more responses are observed in these 36 patients (or if 10 or more responses are observed in the first 18 patients). Posterior estimates of the probability that the response rate exceeds 0.25 will also be calculated assuming a non-informative prior distribution.

- **Substudy 4**

$H_0: p \leq 0.07$ versus $H_A: p > 0.07$.

If there are one or zero patients with a response (defined as a CR or PR) in the first 16 evaluable patients included in the interim analysis in each of Cohort 4a and 4b, the cohort will be stopped. If not, an additional 34 patients will be enrolled, for a total of 50 evaluable patients. The null hypothesis will be rejected if seven or more responses are observed in these 50 patients.

- **Substudy 5**

$H_0: p \leq 0.10$ versus $H_A: p > 0.30$.

If there is one or fewer patient with a response (defined as a CR or PR) in the first 13 evaluable patients included in the interim analysis, the cohort will be stopped. If not, an additional 13 patients will be enrolled, for a total of 26 evaluable patients. The null hypothesis will be rejected if six or more responses are observed in these 26 patients (or if five or more responses are observed in the first 13 patients). Posterior estimates of the probability that the response rate exceeds 0.1 will also be calculated assuming a non-informative prior distribution.

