Confirmation

Confirmation of PR and CR is required approximately 4–5 weeks after the initial scan showing PR or CR.

Duration of overall response

The duration of overall response is measured from the time measurement criteria are first met for CR/PR (whichever is first recorded) until the first date that recurrent or PD is objectively documented (taking as reference for PD the smallest measurements recorded on study).

The duration of overall complete response is measured from the time measurement criteria that are first met for CR until the first date that recurrent disease is objectively documented.

Duration of stable disease

Stable disease is measured from the start of the treatment until the criteria for progression are met, taking as reference the smallest sum on study (if the baseline sum is the smallest, this is the reference for calculation of PD). In this study, the minimum duration for SD is defined as 6 weeks.

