6.3.1. Primary Efficacy Analysis

6.3.1.1. Objective Response Rate

The primary efficacy endpoint in all substudies will be objective response rate (ORR), defined as the achievement of confirmed CR or PR using RECIST 1.1 ([Eisenhauer 2009](#)) as assessed by BICR. Point estimates and exact 2-sided 95% CIs will be provided.

Classification of best confirmed response is done according to the following hierarchy and rules:

1. Complete Response (CR): requires two consecutive CR response assessments a minimum of four weeks apart
2. Partial Response (PR): requires two consecutive PR response assessments OR a PR response immediately followed by a CR response assessment (a minimum of four weeks apart)
3. Stable Disease (SD): requires only one SD response assessment (provided minimum criteria for SD duration met)
4. Non-CR/Non-PD (non-measurable disease patients only): requires only one Non-CR/Non-PD response assessment (provided minimum criteria for Non-CR/Non-PD duration met)
5. Progressive Disease (PD): requires only one PD response assessment

The minimum duration for SD and Non-CR/Non-PD is defined as 6 weeks, where the duration is calculated from the start of treatment until the criteria of SD is met.

The classification as per RECIST 1.1 ([Eisenhauer 2009](#)) is summarized in Table 4.

Table 4: Best overall response when confirmation of CR and PR required.

Overall response		BEST overall response
First time point	Subsequent time point	
CR	CR	CR
CR	PR	SD, PD or PR*
CR	SD	SD provided minimum criteria for SD duration met, otherwise PD
CR	PD	SD provided minimum criteria for SD duration met, otherwise PD
CR	NE	SD provided minimum criteria for SD duration met, otherwise NE
PR	CR	PR
PR	PR	PR
PR	SD	SD
PR	PD	SD provided minimum criteria for SD duration met, otherwise PD
PR	NE	SD provided minimum criteria for SD duration met, otherwise NE
NE	NE	NE

CR = complete response, PR = partial response, SD = stable disease, PD = progressive disease, and NE = inevaluable.

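### Protocol 8.3.4.1 lets a cohort be terminated for futility when the last Stage 1 patient enrols, on an incomplete count of confirmed responses, so the stated power is not guaranteed if that option is used

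*Protocol*

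**What the plan says.** Protocol 8.3.4.1 defines the primary endpoint as ORR, "defined as the achievement of confirmed CR or PR using RECIST 1.1, as assessed by BICR". The same section sets three timing rules for the Stage 1 look:

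- **Earliest and latest look.** Stage 1 patients must "have at least had one post-baseline tumor imaging assessment, but no later than after the completion of Cycle 9", which is about 27 weeks.
- **Last enrolment.** If the required number of BICR responses "has not been observed at the time of enrollment of the last patient to Stage 1, enrollment may be suspended"; the sentence then adds the alternative that "enrollment may be suspended, or the cohort may be terminated due to apparent futility". It sets no follow-up condition.
- **Decision rules.** The mandatory stops apply to the first 35, 18, 16 and 13 evaluable patients in Substudies 1, 3, 4 (each cohort) and 5. SAP 6.3.1.1 uses the same denominators.

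Protocol 8.1 and SAP 6.1.6 treat the same situation differently. If the responses are missing at full Stage 1 enrolment, enrolment may be paused so that all patients are treated "for at least 3 months or until disease progression". Neither mentions termination at that point.

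On timing, Protocol 5.3.3.2.2 places the first on-study scan at week 9, and Table 1 allows 7 days either way. Protocol Appendix 2 states: "Confirmation of PR and CR is required approximately" 4 to 5 weeks after the first scan showing response. SAP 6.3.1.1 sets the minimum gap; a CR, for example, "requires two consecutive CR response assessments a minimum of four weeks apart". Under Protocol 8.2.2 a patient is evaluable only after a post-baseline scan or documented clinical progression.

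**The concern.** The earliest possible confirmed response falls at about week 12 (8 + 4) to week 15 (10 + 5). A patient enrolled on the day of the look has no scan and is normally not yet evaluable. A patient with one scan may have a response but cannot have a confirmed one. A futility count made when the last Stage 1 patient enrols is therefore short of its final value.

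The two-stage error rates in Protocol 8.1 compare the final Stage 1 count with a fixed boundary. Comparing a partial count with the same boundary makes stopping more likely whatever the true response rate. Type I error can only fall, so the damage is one-sided: an active regimen may be dropped because some of its responders are not yet visible.

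**Working it through.** **Inputs (Protocol 8.1, Tables 7 and 8).**

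| Substudy | p0 / p1 | n1, stop if ≤ r1 | Stage 1 rejection e1 | n, reject if ≥ r |
|---|---|---|---|---|
| 1 | 0.21 / 0.34 | 35, 7 | none | 74, 22 |
| 3 | 0.25 / 0.45 | 18, 4 | 10 | 36, 14 |
| 4 (each cohort) | 0.07 / 0.20 | 16, 1 | none | 50, 7 |
| 5 | 0.10 / 0.30 | 13, 1 | 5 | 26, 6 |

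For Substudy 1 the boundary is 7, as in Protocol 8.1 and SAP 6.3.1.1. Protocol 8.3.4.1 says five. Only 7 reproduces the stated error rates; five gives 0.0484 and 0.8138.

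**Step 1: reproduce the plan.** Exact binomial enumeration with complete Stage 1 data gives type I error and power of 0.0463/0.8001, 0.0462/0.8098, 0.0448/0.8027 and 0.0387/0.8189. These match the stated values.

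**Step 2: let the Stage 1 count be incomplete.** Let X be the final number of Stage 1 responders and O the number already confirmed at the look, with O | X ~ Binomial(X, f). Then

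Power(f) = Σx b(x; n1, p1) Σo b(o; x, f) · g(o, x),

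where g = 0 if o ≤ r1; g = 1 if o ≥ e1 (Substudies 3 and 5 only); otherwise g = P{Binomial(n − n1, p1) ≥ r − x}. Every visible shortfall is treated as a stop. If the cohort continues, all Stage 1 responders count at the end.

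| f | Substudy 1 | Substudy 3 | Substudy 4 | Substudy 5 |
|---|---|---|---|---|
| 1.00 | 0.800 | 0.810 | 0.803 | 0.819 |
| 0.90 | 0.765 | 0.785 | 0.762 | 0.797 |
| 0.80 | 0.690 | 0.732 | 0.709 | 0.763 |
| 0.60 | 0.396 | 0.511 | 0.561 | 0.645 |

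Substudy 1 shows why the loss is steep. At p1 the expected Stage 1 count is 35 × 0.34 = 11.9. With 60% visible it is 7.1, practically on the boundary of 7. At f = 0.75 the chance of stopping an active Substudy 1 regimen rises from 0.054 to 0.298, while type I error falls from 0.0463 to 0.030.

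**Step 3: what f might be.** The documents give neither accrual time nor response timing, so these are assumptions: uniform Stage 1 accrual over A = 26 to 78 weeks; 60/30/10% of responses first seen at weeks 9/18/27; confirmation 4.5 weeks later. For a look L weeks after last enrolment, f = Σ w(s) · min{1, max[0, (A + L − s − 4.5)/A]}.

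- L = 0, A = 26: 0.6 × 12.5/26 + 0.3 × 3.5/26 + 0 = 0.33.
- L = 0, A = 78: 0.6 × 64.5/78 + 0.3 × 55.5/78 + 0.1 × 46.5/78 = 0.77.
- L = 9 (one scan each): 0.65 to 0.88.
- L = 13 (three months): 0.81 to 0.94.
- L = 27 (Cycle 9 limit), A = 26: 0.9 + 0.1 × 21.5/26 = 0.98, so the stated power is essentially recovered.

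The steep losses therefore belong to termination at last enrolment. The one-scan and three-month looks are milder.

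**The case against.** A reader might infer that no confirmed response can exist when the last Stage 1 patient enrols, and that the trial therefore does not have its stated power. The documents do not support that. Patients enrolled early in Stage 1 can already be confirmed responders, so the count is incomplete rather than empty. The clause is permissive and offers a pause as the alternative. The mandatory stop is the separate rule on evaluable patients, the look may be as late as about 27 weeks, and the SAP does not carry the termination wording.

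Other points stand in part:

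- The power table is a worst case, because reference to apparent futility implies judgement and not an automatic stop.
- Slower accrual, or accrual interrupted by the 10-patient safety look in Substudies 3 and 5, raises visibility. In Substudy 5 that would place 10 of 13 Stage 1 patients before the pause.
- The interim rules in Protocol 8.3.4.1, and SAP 6.3.1.1 for Substudy 5, omit the word confirmed. Counting unconfirmed responses at the look would reduce the loss. SAP 6.3.1.1 does say confirmed for Substudies 1, 3 and 4, so the basis of the count needs stating either way.
- SAP 3.1 refers the Substudy 1 transition to the IDMC charter, which is not available here. Protocol 4.5.4 lets the sponsor discontinue a cohort at any time. Deleting the clause would not remove that general discretion, but it would take an immature futility stop out of the pre-specified design.

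None of this removes the clause or its conflict with Protocol 8.1 and SAP 6.1.6.

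**Conclusion.** The point holds as a conditional one. Protocol 8.3.4.1 permits termination on a partial count, contradicts its own evaluable-patient rule, and departs from the pause-only wording in Protocol 8.1 and SAP 6.1.6. The stated power of 0.80 to 0.82 is not guaranteed if the option is used.

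The power values at a given visible fraction are exact under independent thinning, with every visible shortfall leading to a stop and a boundary of 7 for Substudy 1. The visible fraction itself (about 33 to 77% at last enrolment) rests wholly on the assumed accrual and response timing, so confidence in the size is lower than confidence in the defect. This should be corrected, mainly because the remedy is cheap.

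**What to change.** 1. In Protocol 8.3.4.1, delete the option to terminate for apparent futility at last Stage 1 enrolment. Keep only the enrolment pause, and align the text with Protocol 8.1 and SAP 6.1.6.
2. In all three places, state that the futility count uses confirmed BICR responses. It should be made only when each of the first n1 evaluable patients has a confirmed response; has progressed, died or ended treatment; or has had the first scan with any pending confirmatory scan resolved. The existing Cycle 9 limit stays.
3. Use one Substudy 1 boundary throughout, since five and seven both appear.

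The cost is wording, plus an enrolment pause about 4 to 5 weeks longer than under the one-scan look. No patients or scans are added.

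This does not capture late responders. Under the assumptions above, a look at 13.5 weeks (9 + 4.5) sees 0.6 + 0.3 × 17/26 + 0.1 × 8/26 = 83% with 26-week accrual and 0.6 + 0.3 × 69/78 + 0.1 × 60/78 = 94% with 78-week accrual. Waiting for the week-18 scan and its confirmation (22.5 weeks) would raise this to 0.9 + 0.1 × 17/26 = 97% and 0.9 + 0.1 × 69/78 = 99%, at the price of a longer pause. That trade-off is for the sponsor to weigh.
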